#### **4.0 Risk/Benefit Assessment**

##### **4.1 Risks and Anticipated Adverse Events:**

Risks: This study is considered mild risk. It entails off-label use of netarsudil, which is approved for reduction of intraocular pressure in patients with open angle glaucoma or ocular hypertension.

A number of complaints and complications are anticipated in patients who have had DSO, regardless of whether they participate in this study. Therefore, the presence or absence of the following anticipated complaints and complications in the study eye will be recorded on the electronic case report form (eCRF) for each exam rather than on separate adverse event forms.

- Complaints of ocular discomfort: (examples include: eye pain, irritation, burning, itching, scratchy feeling, foreign body sensation, tired/fatigued feeling, achy/tender/sore feeling, pressure sensation, tightness, twinge/twitchy feeling, dry eyes, tearing/watering, eye redness) These are expected secondary to corneal decompensation with bullae in the area where Descemet's membrane has been removed and endothelial cells have not yet repopulated.
- Complaints of visual symptoms or disturbances: (examples include: glare or fluctuating vision, haloes around lights, diplopia, blurry, hazy, cloudy, filmy or out of focus vision,

ghosting or shadowing, difficulty reading, difficulty with night driving, floaters, spots in vision, light sensitivity, decreased vision, light reflections from intraocular lens or peripheral iridotomy). These are expected secondary to corneal decompensation with bullae in the area where Descemet's membrane has been removed and endothelial cells have not yet repopulated.

- Increased ptosis is expected secondary to corneal decompensation with bullae in the area where Descemet's membrane has been removed and endothelial cells have not yet repopulated.
- Puffy eyelids are expected secondary to corneal decompensation with bullae in the area where Descemet's membrane has been removed and endothelial cells have not yet repopulated.
- Delayed resolution of corneal haze or edema
- Subconjunctival hemorrhage
- Epithelial defect (within the first month of surgery) is expected secondary to corneal decompensation with bullae in the area where Descemet's membrane has been removed and endothelial cells have not yet repopulated.
- Development of capsular haze
- Superficial punctate keratitis

Anticipated adverse events in subjects who had cataract surgery combined with DSO include cystoid macular edema and capsular haze. Cataract formation or progression is an anticipated adverse event in any eye that was phakic and underwent DSO without combined cataract surgery. These anticipated surgical adverse events will be recorded on the electronic case report form (eCRF) for each exam rather than on separate adverse event forms.

The most common anticipated adverse events associated with use of Rhopressa™ include: eye discomfort, irritation, itching or pain, foreign body sensation, increased tearing, blurry vision, conjunctival hyperemia, conjunctival hemorrhage, eyelid swelling, and verticillata. Additional adverse events reported with use of Rhopressa™ include: reduced visual acuity, allergic conjunctivitis, dry eye, keratitis, conjunctival swelling, photophobia, and corneal staining.

Adverse events: The type, severity, duration and frequency of the following anticipated adverse experiences and any other unanticipated ocular adverse events will be tabulated. If a patient experiences an adverse reaction, appropriate medical treatment will be provided. Examples may include:

- Intraocular pressure elevation which requires intervention
- Development of capsular haze which requires intervention
- Cystoid macular edema
- Iritis

Anticipated rare adverse events include retinal detachment, iris synechiae/atrophy, epiretinal membrane, infectious keratitis or conjunctivitis, branch retinal vein occlusion, or endophthalmitis.

Serious Adverse Event: A serious adverse event is one that results in any of the following outcomes: death, a life-threatening adverse event, inpatient hospitalization or prolongation of existing hospitalization, a persistent or significant disability/ incapacity, or a congenital anomaly/birth defect. In the event of a serious adverse event, the investigator will maintain complete documentation and promptly inform the study drug manufacturer and the governing Institutional Review Board (IRB) of the serious adverse event within their required reporting period.

Fellow eye: Patients in this population tend to be affected with the eye condition bilaterally, so many of the study subjects may undergo surgery on the fellow eye during study participation. Routine fellow-eye post-surgical complications will not be transcribed to the eCRF unless the fellow eye is enrolled in the study at the time of the event.

**4.2 Protection Against Risks:** Every effort will be made to minimize any risks or discomforts to study subjects. The investigator will ensure appropriate training of study personnel and monitoring of subjects and will provide appropriate treatment for eye-related adverse events or referral for treatment of non-eye-related adverse events. The subject and or

their health insurance plan will be responsible for payment for treatment, counseling or follow up.

The **Data Safety Monitoring Committee (DSMC)** will be chaired by [name], an independent ophthalmologist practicing in Menasha, Wisconsin. The DSMC will review any serious adverse events as they occur. The DSMC will also review the interim data (including adverse events and subject compliance) every 6 months, to determine if any modifications to the original study plan may be warranted. The DSMC meeting minutes and recommendations will be documented and shared with IRBCo, Inc. and with the provider of the investigational product, Aerie Pharmaceuticals.

**4.3 Potential Benefits to the Subjects:** Study subjects may not realize any direct benefit from participation in the research; rather, important knowledge which may benefit future subjects is being sought. A potential benefit will be either healing or more rapid healing of the endothelial cell defect and avoidance of corneal transplant such as DMEK or DSEK which often require long term use of topical corticosteroids and the risk of secondary glaucoma.

**4.4 Study termination:** The study may be prematurely terminated if, in the opinion of the investigator or the Sponsor, there is sufficient reasonable cause. Written notification, documenting the reason for study termination, will be provided to the investigator or Sponsor by the terminating party. Circumstances that may warrant termination include, but are not limited to:

- Determination of unexpected, significant, or unacceptable risk to subjects.
- Insufficient adherence to protocol requirements.
- Data that is not sufficiently complete or evaluable.
- Plans to modify, suspend or discontinue marketing of the Study Product.

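### Ten of the 11 most common netarsudil effects fall under a present/absent recording rule, so the arms can be compared on incidence but not on severity or dated duration

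*Combined protocol and SAP*

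**What the plan says.** All of the recording rules are in Section 4.1 of the combined protocol and SAP.

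- **Recording rule.** For complaints and complications anticipated after DSO, "the presence or absence of the following anticipated complaints and complications in the study eye will be recorded on the electronic case report form". This is done "for each exam rather than on separate adverse event forms". No grade and no onset or resolution date is requested.
- **Presumed cause.** Five of the nine bullets on that list (ocular discomfort, visual symptoms, ptosis, puffy eyelids, epithelial defect) carry a statement such as "These are expected secondary to corneal decompensation with bullae in the area where Descemet's membrane has been removed". The other four do not.
- **Known drug effects.** The most common Rhopressa events "include: eye discomfort, irritation, itching or pain, foreign body sensation, increased tearing, blurry vision, conjunctival hyperemia, conjunctival hemorrhage, eyelid swelling, and verticillata".
- **Tabulation.** "The type, severity, duration and frequency of the following anticipated adverse experiences and any other unanticipated ocular adverse events will be tabulated". The examples given are raised intraocular pressure and capsular haze, each when it needs intervention, cystoid macular edema, and iritis.
- **Combined cataract surgery.** Cystoid macular edema and capsular haze are anticipated in these eyes, and "These anticipated surgical adverse events will be recorded on the electronic case report form (eCRF) for each exam rather than on separate adverse event forms".

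Elsewhere, Section 3.1 has slit-lamp findings documented and visual acuity measured at each visit. Section 4.2 has the DSMC review interim data, including adverse events, every 6 months. Section 3.2 describes no between-arm safety analysis.

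**The concern.** The symptoms that netarsudil is known to cause are largely the symptoms expected from the surgery. When drug and procedure produce the same complaint, many eyes in both arms may report it, and the arms may then differ mainly in how bad it is and how long it lasts. The recording rule does not ask for either. At a given exam, a severe reaction and a mild one produce the same entry.

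The use is off-label, so a reader will want to know how well the drop is tolerated on an eye that has just had DSO. If netarsudil makes common symptoms worse or more prolonged without making them much more frequent, the data as specified would show little of it.

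**Working it through.** **1. Overlap of the two lists (Section 4.1)**

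| Common Rhopressa term | Match on the present/absent list | Bullet attributed to decompensation? |
|---|---|---|
| Discomfort | Ocular discomfort | Yes |
| Irritation | Ocular discomfort | Yes |
| Itching | Ocular discomfort | Yes |
| Pain | Ocular discomfort | Yes |
| Foreign body sensation | Ocular discomfort | Yes |
| Increased tearing | Ocular discomfort | Yes |
| Blurry vision | Visual symptoms | Yes |
| Conjunctival hyperemia | Eye redness, under ocular discomfort | Yes |
| Eyelid swelling | Puffy eyelids | Yes |
| Conjunctival hemorrhage | Subconjunctival hemorrhage | No |
| Verticillata | None | – |

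This gives 10 of 11 on the list, 9 of those 10 under an attributed bullet. Of the seven additional Rhopressa events, three are clearly on the list (reduced acuity, dry eye, photophobia) and two partly, through superficial punctate keratitis. In total 10 + 3 = 13 of 18 match clearly, and 15 of 18 with partial matches.

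**2. What the plan still captures**

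- *Incidence by arm:* yes, from the per-exam entries.
- *Duration:* coarsely. There are up to seven post-operative exams (day 1; weeks 1, 3, 5, 7, 9, 12). From week 1 the gaps are 2 weeks, then 3 weeks at the end. After healing is noted at week 3, 5 or 7 the next exam may be omitted, which widens a gap to 4 or 5 weeks (3 to 7, 5 to 9, 7 to 12).
- *Signs:* hyperemia, punctate keratitis and other surface toxicity by slit lamp at each visit, with no grading scale.
- *Vision:* acuity at each visit and a visual disability questionnaire at screening and from week 3 (Table 1). These bear indirectly on blur.
- *Severity of discomfort, irritation, itching, pain, foreign body sensation or tearing:* not requested.

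**3. Arm size**

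The plan gives no safety sample size or safety power. Its figure for the primary endpoint (Section 3.2) supplies the arm size: n = 2(1.645 + 0.842)² × (0.30/0.20)² = 27.8, so 28 per arm by normal approximation. The t-test gives 29 (power 0.806), which matches the plan. With 3% dropout, 58/0.97 = 59.8, so 60.

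**4. Illustration: sensitivity of present/absent data to background**

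All event rates here are assumptions. Let s be the surgical background rate and d the proportion of eyes in which the drug independently causes the symptom. The netarsudil rate is p₂ = 1 − (1 − s)(1 − d). With 30 per arm, two-sided 5%, and p̄ = (s + p₂)/2:

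power = Φ{[(p₂ − s) − 1.96√(2p̄(1 − p̄)/n)] / √([s(1 − s) + p₂(1 − p₂)]/n)}

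For s = 0.10 and d = 0.50: p₂ = 0.55, p̄ = 0.325, and (0.45 − 0.237)/0.106 = 2.01, so power is 0.978.

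| Background s | d = 0.50: normal / Fisher | d = 0.20: normal / Fisher |
|---|---|---|
| 0.10 | 0.978 / 0.962 | 0.425 / 0.305 |
| 0.30 | 0.790 / 0.714 | 0.199 / 0.133 |
| 0.50 | 0.517 / 0.413 | 0.118 / 0.075 |
| 0.70 | 0.282 / 0.192 | 0.075 / 0.043 |
| 0.90 | 0.109 / 0.019 | 0.045 / 0.008 |

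**5. Illustration: pooling under a heading**

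Using the same normal-approximation formula with 29 per arm and one-sided 5% (1.645 for 1.96), one term rising from 30% to 60% is detected with 75% power. The proportion free of the symptom falls by the factor 0.40/0.70. If the only entry is a heading already positive in 50%, 70% or 90% of control eyes, the same factor gives netarsudil rates of 71%, 83% and 94% (for example 1 − 0.10 × 0.40/0.70 = 0.943), and power of 51%, 31% and 15%.

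Steps 4 and 5 measure lost sensitivity for incidence. They do not measure the loss from missing grades and dates, which follows from the recording rule itself.

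**The case against.** The strongest case is that the trial has a concurrent, randomized, masked vehicle arm. Incidence can be compared whatever cause the protocol presumes, so attributing symptoms to surgery does not by itself bias the comparison. Repeated entries give some duration, and slit-lamp signs and acuity are collected at every visit. The plan also gives a reason for its route: these complaints are anticipated after DSO whether or not the patient takes part. All of this stands. A reader might infer that the trial cannot show drug toxicity at all; the documents do not support that, and step 4 shows good power for a large excess over a low background.

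A reader might also infer that the plan contradicts itself by promising severity and duration for symptoms it only ticks. The tabulation sentence most naturally governs the examples after it plus unanticipated ocular events, and the surface symptoms are not among those examples. The examples are introduced loosely, so the scope is not fully closed, but for the drug symptoms this is a gap and not a conflict.

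Three further readings go too far:

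- *That the DSMC would see nothing of these events.* Section 4.2 speaks of interim data including adverse events, which does not exclude eCRF items. It does not say that they are shown either.
- *That each heading is a single tick.* The eCRF is not in the documents, so step 5 is conditional.
- *That capsular haze is in conflict.* The tabulated example is limited to haze needing intervention, which is a threshold.

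For cystoid macular edema no such threshold is stated. An eCRF could hold severity and dates, so the tabulation is not shown to be impossible, but the route is unclear.

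**Conclusion.** The point holds as a weakness in safety data capture. The recording rule covers 10 of the 11 most common netarsudil effects, so the trial as written can compare their incidence by arm but not their severity or dated duration. Ungraded slit-lamp signs and the vision measures fill only part of the gap, and they do not cover symptoms such as pain, irritation or itching.

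How much sensitivity for incidence is also lost depends on a background rate the documents do not give. Under the assumed rates, power for a drug effect in half of eyes runs from about 0.98 at 10% background to 0.11 at 90% (normal approximation). These figures treat eyes as independent, although Section 3.1 lets a second eye enter the opposite arm. They also ignore open-label netarsudil, which placebo eyes may receive after the 5-week exam and which would further blur the later comparison.

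The one place where the passages need reconciling is cystoid macular edema after combined cataract surgery. The overlap count rests on matching hyperemia to eye redness and eyelid swelling to puffy eyelids.

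**What to change.** 1. Keep the eCRF route, but record each Rhopressa term in Section 4.1 as its own item, with a severity grade (for example 0–3) and onset and resolution dates.
2. Tabulate these items by randomized arm, showing time before and after any open-label switch separately, and include the table in the DSMC's 6-monthly review.
3. State one recording route for cystoid macular edema, so that the combined-surgery paragraph and the tabulation sentence agree. Make clear that capsular haze moves to the tabulated list only when it requires intervention.

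The cost is a few extra eCRF fields and one safety table, with no new visits, staff or tests. It is a cheap improvement and should be made.

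### The serious adverse event definition has no sight-threatening or medically important category, so some grave eye events treated without admission have no stated expedited route and may reach the DSMC only at its 6-monthly review

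*Combined protocol and SAP*

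**What the plan says.** Section 4.1 (Risks and Anticipated Adverse Events) opens its definition: "A serious adverse event is one that results in any of the following outcomes: death, a life-threatening adverse event, inpatient hospitalization". After prolongation of an existing stay, it ends with "a persistent or significant disability/ incapacity, or a congenital anomaly/birth defect". That makes five outcomes and no others.

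The same section names the gravest eye complications it foresees: "Anticipated rare adverse events include retinal detachment, iris synechiae/atrophy, epiretinal membrane, infectious keratitis or conjunctivitis, branch retinal vein occlusion, or endophthalmitis". It does not say whether any of them is to be treated as serious.

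The reporting routes are:

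- **IRB and manufacturer (4.1).** For a serious event, the investigator will "promptly inform the study drug manufacturer and the governing Institutional Review Board (IRB) of the serious adverse event within their required reporting period".
- **DSMC, as events arise (4.2, Protection Against Risks).** "The DSMC will review any serious adverse events as they occur".
- **DSMC, periodic (4.2).** "The DSMC will also review the interim data (including adverse events and subject compliance) every 6 months".
- **Onward from the DSMC (4.2).** "The DSMC meeting minutes and recommendations will be documented and shared with IRBCo, Inc. and with the provider of the investigational product".
- **Adverse events generally (4.1).** Anticipated experiences and "any other unanticipated ocular adverse events will be tabulated", with no timeline attached.

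**The concern.** This is an eye-drop trial after corneal surgery, run through clinic visits, in which netarsudil is used off-label (4.1). The harms most likely to call for a pause are those that threaten the study eye. The definition reaches them only if they lead to admission, threaten life, or are judged disabling.

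An event can be grave for the eye and meet none of these. Infectious keratitis or endophthalmitis that is treated early in clinic, with vision preserved, is an example. One such case may mean little. Several in a short time are what an independent committee should see promptly, and the protocol gives them no stated path to the DSMC ahead of its periodic meeting. Randomization could continue meanwhile without independent review of those events.

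**Working it through.** The only plan figure involved is the DSMC interval of 6 months. It is stated, not derived, so there is nothing to reproduce. The check is mainly a tracing of the text.

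**Step 1. Take an event named in 4.1 (for example, infectious keratitis in a study eye) that is managed without admission, and test it against the list.**

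| Limb of the definition | Met? |
|---|---|
| Death | No |
| Life-threatening event | Not by the eye event in itself |
| Hospitalization or its prolongation | No, by the premise |
| Persistent or significant disability/incapacity | Depends on visual outcome and on judgement |
| Congenital anomaly/birth defect | No |

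Classification therefore rests on the disability limb alone.

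**Step 2. Ask how far that limb reaches.** Its two adjectives are alternatives. Significant visual incapacity can qualify at once, without admission and without proof that it lasts. An event that resolves with vision preserved does not qualify. Between these, the protocol gives no visual-loss criterion. Section 4.1 also lists decreased and hazy vision among the complaints expected after Descemet stripping, to be recorded on the eCRF and not on separate adverse event forms. Visual loss is thus a hard marker to apply in these eyes.

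**Step 3. Follow the routes.**

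| | Judged serious | Not judged serious |
|---|---|---|
| IRB and manufacturer | Prompt notice (4.1) | No prompt notice stated; DSMC minutes and recommendations shared later (4.2) |
| DSMC | As it occurs (4.2) | Periodic review every 6 months (4.2) |

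No other section gives the listed eye events a faster path.

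**Step 4. Size the interval.** Follow-up is 12 weeks, with an exit window of ± 2 weeks (Table 1).

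- 6 months = 365.25 / 2 / 7 = 26.1 weeks
- Against the 12-week exit: 26.1 / 12 = 2.2
- Against the latest exit in the window, 12 + 2 = 14 weeks: 26.1 / 14 = 1.9

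Even at the latest exit, one DSMC interval is nearly twice a subject's participation. The 26 weeks is the longest wait, for an event just after a meeting. If events fell evenly over the interval (an assumption), the mean wait would be 26.1 / 2 = 13 weeks.

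**The case against.** The strongest reply is that the disability limb already covers the cases that matter. Endophthalmitis or retinal detachment with major visual loss can be called serious immediately, admitted or not. That is correct. A reader might infer that all such events escape expedited review unless the subject is admitted, or that they become serious only once loss has proved lasting. The wording supports neither inference. The limb still does not reach an event that resolves, and it leaves the rest to judgement without a criterion.

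Other points against the concern:

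- **Anticipated does not mean non-serious.** A reader might infer that listing these events as anticipated and rare removes them from the serious class. The label describes expectedness, and nothing in 4.1 stops an anticipated event from also being serious. This stands.
- **Six months is the DSMC interval only.** A reader might apply it to the IRB and manufacturer. The documents give no interval for those bodies when an event is not serious; they simply state no prompt notice. This stands.
- **Local action remains possible.** Adverse events are recorded at every visit, 2.7 refers to a single study site, and 4.4 lets the investigator or sponsor stop the study for unexpected, significant or unacceptable risk without waiting for the DSMC. A cluster could be noticed and acted on. This lessens the concern but does not replace independent review.
- **Transplantation after failed clearing.** A reader might want a corneal graft for non-clearing counted as serious too. The documents do not support adding it here. Sections 1.2 and 4.1 foresee incomplete or delayed clearing, it lies close to the efficacy outcome, and nothing shows that it would be rare.
- **No count of subjects at risk.** Any figure for subjects randomized between meetings needs an accrual rate, which the documents do not give, and would not measure events missed.

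**Conclusion.** The concern holds in a limited form. The definition is closed and has no sight-threatening or medically important category. Endophthalmitis, infectious keratitis, retinal detachment or retinal vein occlusion in a study eye has no stated expedited route if it is managed without admission and not judged a persistent or significant disability. It may then reach the DSMC only at the periodic review, up to about 26 weeks later, against a 12-week follow-up.

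This is a stated rule that can delay independent review when followed exactly, so it is more than a missing detail. It should be changed, although the trial does not fail without the change. The conclusion assumes that such an event can be managed without admission and that no faster route exists in arrangements outside these documents. The size is a possible delay, not a number of cases, and it does not affect the power calculation or the analysis.

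**What to change.** Add one limb to the definition in 4.1: *or any sight-threatening or medically important event in a study eye, including endophthalmitis, infectious keratitis, retinal detachment and retinal vascular occlusion, whether or not the subject is hospitalized.*

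These events would then follow the routes the protocol already has: DSMC review as they occur, and prompt notice to the IRB and manufacturer. Unplanned return to surgery and transplantation for non-clearing should be left out of this sentence.

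The cost is one sentence and a few more expedited reports of events that 4.1 itself calls rare. No visit, procedure, sample size or treatment rule changes. Some judgement remains over what else counts as medically important, but the named events no longer depend on it.
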